7 ADVERSE EVENTS

7.1 Definitions

An *Adverse Event (AE)* is defined as any new untoward medical occurrence or worsening of a pre-existing medical condition in a patient or clinical investigation subject administered an investigational (medicinal) product and that does not necessarily have a causal relationship with this treatment. An AE can therefore be any unfavorable and unintended sign (including an abnormal laboratory finding, for example), symptom, or disease temporally associated with the use of investigational product, whether or not considered related to the investigational product.

7.1.1 Serious Adverse Events

A *serious AE (SAE)* is any untoward medical occurrence that at any dose:

- results in death
- is life-threatening (defined as an event in which the subject was at risk of death at the time of the event; it does not refer to an event which hypothetically might have caused death if it were more severe)
- requires inpatient hospitalization or causes prolongation of existing hospitalization (see note below for exceptions)
- results in persistent or significant disability/incapacity
- is a congenital anomaly/birth defect
- is an important medical event (defined as a medical event(s) that may not be immediately life-threatening or result in death or hospitalization but, based upon appropriate medical and scientific judgment, may jeopardize the subject or may require intervention [eg, medical, surgical] to prevent one of the other serious

outcomes listed in the definition above.) Examples of such events include, but are not limited to, intensive treatment in an emergency room or at home for allergic bronchospasm; blood dyscrasias or convulsions that do not result in hospitalization.)

Suspected transmission of an infectious agent (eg, any organism, virus or infectious particle, pathogenic or non-pathogenic) via the study drug is an SAE and must be reported accordingly.

Although overdose and cancer are not always serious by regulatory definition, these events should be reported on an SAE form and sent to BMS in an expedited manner.

All pregnancies, regardless of outcome, must be reported to the sponsor on a Pregnancy Surveillance Form, not an SAE form (see Section 7.6).

NOTE:

The following hospitalizations are not considered SAEs in BMS clinical studies:

- a visit to the emergency room or other hospital department < 24 hours, that does not result in admission (unless considered "important medical event" or event life threatening)
- elective surgery, planned prior to signing consent
- admissions as per protocol for a planned medical/surgical procedure
- routine health assessment requiring admission for baseline/trending of health status (eg, routine colonoscopy)
- medical/surgical admission for purpose other than remedying ill health state and was planned prior to entry into the study. Appropriate documentation is required in these cases
- admission encountered for another life circumstance that carries no bearing on health status and requires no medical/surgical intervention (eg, lack of housing, economic inadequacy, care-giver respite, family circumstances, administrative)

7.1.2 Nonserious Adverse Events

All AEs that are not classified as serious.

7.2 Assignment of Adverse Event Intensity and Relationship to Study Drug

The following categories and definitions of intensity as determined by a physician should be used for all BMS clinical study AEs:

- Mild (Grade 1) - Awareness of event but easily tolerated
- Moderate (Grade 2) - Discomfort enough to cause some interference with usual activity
- Severe (Grade 3) - Inability to carry out usual activity
- Very Severe (Grade 4) - Debilitating, significantly incapacitates subject despite symptomatic therapy

The following categories and definitions of causal relationship to study drug as determined by a physician should be used for all BMS clinical study AEs:

- Related: There is a reasonable causal relationship to study drug administration and the AE
- Not related: There is not a reasonable causal relationship to study drug administration and the AE

The expression "reasonable causal relationship" is meant to convey in general that there are facts (eg, evidence such as de-challenge/re-challenge) or other arguments to suggest a positive causal relationship.

7.3 Collection and Reporting

Adverse events can be spontaneously reported or elicited during open-ended questioning, examination, or evaluation of a subject. (In order to prevent reporting bias, subjects should not be questioned regarding the specific occurrence of one or more AEs.)

If known, the diagnosis of the underlying illness or disorder should be recorded, rather than its individual symptoms. The following information should be captured for all AEs: onset, duration, intensity, seriousness, relationship to study drug, action taken, and treatment required. If treatment for the AE was administered, it should be recorded on the

appropriate CRF page. The investigator shall supply the sponsor and Ethics Committee with any additional requested information, notably for reported deaths of subjects.

Completion of supplemental CRFs may be requested for AEs and/or laboratory abnormalities that are reported/identified during the course of the study.

7.3.1 Serious Adverse Events

Following the subject's written consent to participate in the study, all SAEs must be collected, including those thought to be associated with protocol-specified procedures. All SAEs must be collected that occur within 30 days of discontinuation of dosing or within 30 days of the last visit for screen failures. If applicable, SAEs must be collected that relate to any later protocol-specified procedure (eg, a follow-up skin biopsy).

The investigator should notify BMS (or designee) of any SAE occurring after these time periods that is believed to be related to study drug or protocol-specified procedure.

Serious adverse events, whether related or unrelated to study drug, must be recorded on the SAE page of the CRF and reported within 24 hours to BMS (or designee) to comply with regulatory requirements. An SAE report should be completed for any event where doubt exists regarding its status of seriousness.

All SAEs must be reported within 24 hours by confirmed facsimile transmission (fax). If only limited information is initially available, follow-up reports are required. (Note: Follow-up SAE reports should include the same investigator term(s) initially reported.) In selected circumstances, the protocol may specify conditions that require additional telephone reporting. The SAE electronic CRF in the electronic data capture tool should not be used.

If the investigator believes that an SAE is not related to study drug, but is potentially related to the conditions of the study (such as withdrawal of previous therapy, or a complication of a study procedure), the relationship should be specified in the narrative section of the SAE page of the CRF.

If an ongoing SAE changes in its intensity or relationship to study drug, a follow-up SAE report should be sent within 24 hours to the sponsor (or designee). As follow-up

information becomes available it should be sent within 24 hours using the same procedure used for transmitting the initial SAE report. All SAEs should be followed to resolution or stabilization.

SGS Contact Information:

SAE Facsimile Number: PPD

SAE Telephone Contact (24h emergency phone number): PPD

7.3.2 Handling of Expedited Safety Reports

In accordance with local regulations, BMS will notify investigators of all SAEs that are suspected (related to the investigational product) and unexpected (ie, not previously described in the Investigator Brochure). In the European Union (EU), an event meeting these criteria is termed a Suspected, Unexpected Serious Adverse Reaction (SUSAR). Investigator notification of these events will be in the form of an expedited safety report (ESR).

Other important findings which may be reported by the sponsor as an ESR include: increased frequency of a clinically significant expected SAE, an SAE considered associated with study procedures that could modify the conduct of the study, lack of efficacy that poses significant hazard to study subjects, clinically significant safety finding from a nonclinical (eg, animal) study, important safety recommendations from a study data monitoring committee, or sponsor decision to end or temporarily halt a clinical study for safety reasons.

Upon receiving an ESR from BMS, the investigator must review and retain the ESR with the Investigator Brochure. Where required by local regulations or when there is a central IRB/IEC for the study, the sponsor will submit the ESR to the appropriate IRB/IEC. The investigator and IRB/IEC will determine if the informed consent requires revision. When BMS has a written agreement with a local IRB/IEC, BMS will directly submit ESR(s). The investigator should also comply with the IRB/IEC procedures for reporting any other safety information.

In addition, suspected serious adverse reactions (whether expected or unexpected) shall be reported by BMS to the relevant competent health authorities in all concerned countries according to local regulations (either as expedited and/or in aggregate reports).

7.3.3 Nonserious Adverse Events

The collection of nonserious AE information should begin at initiation of study drug. Nonserious AE information should also be collected from the start of a placebo lead-in period or other observational period intended to establish a baseline status for the subjects.

If an ongoing nonserious AE worsens in its intensity or its relationship to the study drug changes, a new nonserious AE entry for the event should be completed. Nonserious AEs should be followed to resolution or stabilization, or reported as SAEs if they become serious (see Section 7.3.1). Follow-up is also required for nonserious AEs that cause interruption or discontinuation of study drug, or those that are present at the end of study treatment as appropriate.

All identified nonserious AEs must be recorded and described on the appropriate nonserious AE page of the CRF (paper or electronic).

7.4 Laboratory Test Abnormalities

All laboratory test values captured as part of the study should be recorded on the appropriate laboratory test results pages of the CRF, or be submitted electronically from a central laboratory. In addition, the following laboratory abnormalities should also be captured on the nonserious AE CRF page (paper or electronic) or SAE paper CRF page as appropriate:

- Any laboratory test result that is clinically significant or meets the definition of an SAE
- Any laboratory abnormality that required the subject to have study drug discontinued or interrupted
- Any laboratory abnormality that required the subject to receive specific corrective therapy

It is expected that wherever possible, the clinical, rather than the laboratory term would be used by the reporting investigator (eg, anemia versus low hemoglobin value).

7.5 Overdose

An overdose is defined as the accidental or intentional ingestion or infusion of any dose of a product that is considered both excessive and medically important. All occurrences of overdose must be reported as an SAE (see Section 7.3.1 for reporting details.)

7.6 Pregnancy

Sexually active WOCBP must use an effective method of birth control during the course of the study, in a manner such that risk of failure is minimized (See Section 4.2.1 for the definition of WOCBP).

Before enrolling WOCBP in this clinical study, investigators must review the sponsor-provided information about study participation for WOCBP. The topics include the following:

- General Information
- Informed Consent Form
- Pregnancy Prevention Information Sheet
- Drug Interactions with Hormonal Contraceptives
- Contraceptives in Current Use
- Guidelines for the Follow-up of a Reported Pregnancy

Prior to study enrollment, WOCBP must be advised of the importance of avoiding pregnancy during study participation and the potential risk factors for an unintentional pregnancy. The subject must sign an informed consent form documenting this discussion.

7.6.1 Requirements for Pregnancy Testing

All WOCBP MUST have a **negative** pregnancy test within 24 hours as specified in Section 6.1 **prior** to receiving the investigational product. The minimum sensitivity of the pregnancy test must be 25 IU/L or equivalent units of HCG. If the pregnancy test is

positive, the subject must not receive the investigational product and must not continue in the study.

Pregnancy testing must also be performed throughout the study as specified in Section 6.1 (see flow chart/time and events schedule) and the results of all pregnancy tests (positive or negative) recorded on the CRF or transferred electronically.

In addition, all WOCBP should be instructed to contact the investigator immediately if they suspect they might be pregnant (eg, missed or late menstrual period) at any time during study participation.

7.6.2 Reporting of Pregnancy

If, following initiation of the investigational product, it is subsequently discovered that a study subject is pregnant or may have been pregnant at the time of investigational product exposure, including during at least 6 half-lives after product administration, the investigational product will be permanently discontinued in an appropriate manner (eg, dose tapering if necessary for subject safety). The investigator must immediately notify the SGS medical monitor of this event, record the pregnancy on the Pregnancy Surveillance Form (not an SAE form). Initial information on a pregnancy must be reported immediately to SGS and the outcome information provided once the outcome is known. Completed Pregnancy Surveillance Forms must be forwarded to SGS according to SAE reporting procedures described in Section 7.3.1.

Protocol-required procedures for study discontinuation and follow-up must be performed on the subject unless contraindicated by pregnancy (eg, x-ray studies). Other appropriate pregnancy follow-up procedures should be considered if indicated. Follow-up information regarding the course of the pregnancy, including perinatal and neonatal outcome must be reported on the Pregnancy Surveillance Form.

Any pregnancy that occurs in a female partner of a male study participant should be reported to the sponsor. Information on this pregnancy will be collected on the Pregnancy Surveillance Form.

7.7 Other Safety Considerations

Any significant worsening noted during interim or final physical examinations, electrocardiograms, x-rays, and any other potential safety assessments, whether or not these procedures are required by the protocol, should also be recorded on the appropriate nonserious AE page of the CRF (paper or electronic) or SAE paper CRF page.

8 STATISTICAL CONSIDERATIONS

8.1 Sample Size Determination

The sample size evaluation is based on the primary objective of the study, to assess the antiviral activity of BMS-626529 following administration of selected regimens of BMS-663068 with and without RTV administered orally to HIV infected subjects for 8 days. A mean decrease from baseline in HIV RNA of at least 1 log₁₀ at Day 9 within any one regimen group may suggest that the dose of BMS-663068 is sufficiently active against HIV to proceed with further development of the drug. If the BMS-663068 containing regimen has no effect, then administration of the regimen to 10 subjects (ARV naive or experienced) would provide a ≤1% probability to observe a mean log₁₀ drop of ≥1. If the true population mean decrease from baseline in HIV RNA is ≥1.5 log₁₀, then there would be a 99% probability that the observed mean decline from baseline would be ≥1 log₁₀. In addition, 10 subjects within each group can also provide >99% power to conclude the mean decreases in log₁₀ HIV RNA from baseline > 0 if the true population decrease from that group is 1 log₁₀. Meanwhile, 10 subjects in each group can also provide 82% power to conclude the mean decreases in log₁₀ HIV RNA from two groups are different if the true difference in population mean decreases from these two groups is 0.6 log₁₀.

In addition, administration of the BMS-663068 containing regimen to 10 subjects per group provides an 80% probability of observing at least one occurrence in that regimen group of any adverse event that would occur with 15% incidence in the population from which the sample is drawn.

For these calculations, it is assumed that the \log_{10} decrease in HIV RNA from baseline to Day 9 is normally distributed, with a standard deviation of 0.5, as estimated from AI430003.

8.2 Populations for Analyses

All subjects who receive study medication will be included in the safety data set.

All available data from subjects who receive BMS-663068 will be included in the pharmacokinetic data set.

All available data from subjects for whom pharmacodynamic measurements are available at baseline and at least one other time will be included in the pharmacodynamic data set.

8.3 Endpoint Definitions

8.3.1 Safety Endpoint

Safety assessments will be based on adverse event reports and the results of vital sign measurements, ECGs, physical examinations, and clinical laboratory tests. The incidence of adverse events will be tabulated and reviewed for potential significance and clinical importance.

8.3.2 Pharmacokinetic Endpoint(s)

Pharmacokinetics of BMS-626529 and RTV will be derived from plasma concentration versus time data. The pharmacokinetic parameters to be assessed include:

C _{max}	Maximum observed plasma concentration
C _{trough}	Trough observed plasma concentration
T _{max}	Time of maximum observed plasma concentration
AUC(TAU)	Area under the concentration-time curve in one dosing interval
AUC(0-24h)	Area under the concentration-time curve over a 24-hour period following the AM dose (PM for Group 2) on Day 8
C _{ss,avg}	Average steady-state plasma concentration, calculated as $AUC(0-24h)/24$
T-HALF	Terminal half-life (after last dose only)
CLT/F	Apparent total body clearance

V _{ss} /F	Apparent volume of distribution at steady-state
AI	Accumulation index; ratio of AUC(TAU) at steady-state to AUC(TAU) after the first dose
Protein binding (%)	Percent of BMS-626529 that are bound to total plasma proteins
IQ	Inhibitory quotient, calculated as the ratio of BMS-626529 in vivo exposure to in vitro measured protein binding adjusted EC ₉₀ . The following in vivo exposure measures will be used in evaluating IQ: C _{max} , C _{trough} and C _{ss,avg} .

Individual subject pharmacokinetic parameter values will be derived by non compartmental methods by a validated pharmacokinetic analysis program.

8.3.3 Pharmacodynamic Endpoint(s)

Pharmacodynamic assessment will be based on change in HIV RNA. Additionally, CD4+ and CD8+ lymphocyte counts and percents will be assessed.

8.4 Analyses

8.4.1 Demographics and Baseline Characteristics

Frequency distributions of gender and race will be tabulated. Summary statistics for age, body weight, height, and Body Mass Index (BMI) will be tabulated.

8.4.2 Safety Analyses

All recorded adverse events will be listed and tabulated by system organ class, preferred term and treatment. Vital signs and clinical laboratory test results will be listed and summarized by treatment. Any significant physical examination findings, and clinical laboratory results will be listed. ECG readings will be evaluated by the investigator and abnormalities, if present, will be listed.

8.4.3 Efficacy Analyses

Not Applicable.

8.4.4 Pharmacokinetic Analyses

The multiple-dose pharmacokinetics of BMS-626529 following administration of BMS-663068 with or without RTV will be described by summary statistics for the pharmacokinetic parameters by regimen group, study day, dose time (AM or PM, Groups 1, 3, 4 and 5 only), antiretroviral treatment history (ARV naive, ARV experienced, and combined [ARV naive + ARV experienced]). Medians and ranges will be presented for Tmax. Means and standard deviations will be provided for T-HALF. Geometric means and coefficients of variation will be presented for Cmax, Ctrough, C_{ss,avg}, AUC(TAU), AUC(0-24), CLT/F, V_{ss}/F and AI.

To assess the dependency on regimen, scatter plots of Cmax, AUC(TAU), and Ctrough versus regimen group will be provided by day and dose time (Groups 1, 3, 4 and 5 only). Time to steady-state will be evaluated by summary statistics of Ctrough (following AM doses except Group 2) by study day and by plot of geometric mean Ctrough versus study day.

Protein binding (%) for BMS-626529 will be evaluated by summary statistics and tabulated by regimen group. Inhibitory Quotient (IQ) of Cmax, Ctrough (both on Day 8 following AM regimens except Group 2) and C_{ss,avg} of BMS-626529 (defined in section 8.3.2) will be summarized and tabulated by regimen group.

Point estimates and 90% confidence intervals will be constructed for accumulation indices (ratio of Day 8 [AM doses except Group 2] vs. Day 1 for AUC(TAU), Cmax and Ctrough) by regimen group. These estimates will be generated using general linear models fitted to log-transformed data with study day as a fixed effect, and measurements within each subject as repeated measurements. Point estimates and 90% confidence intervals for differences at the log-scale will be exponentiated to obtain estimates and confidence intervals for ratios of geometric means in the original scale. No adjustments will be made for multiplicity.

Similar analysis will be used to assess the effect of RTV on PK exposure of BMS-626529, by comparing the exposure of BMS-626529 in group 3 vs. group 5 and group 4 vs. group 5 with regimen groups as a fixed effect in the general linear models. The effects of diurnal PK variation (PM vs. AM) will also be assessed by the similar model for

Groups 1, 3, 4 and 5 only with time point (PM or AM) as a fixed effect and measurements within each subject as repeated measurements in the general linear models.

The multiple-dose pharmacokinetics of RTV when coadministered with various regimens of BMS-663068 will be described by summary statistics for the pharmacokinetic parameters by regimen group, study day, dose time (AM or PM, Groups 1 and 3), antiretroviral treatment history (ARV naive, ARV experienced, and combined [ARV naive + ARV experienced]). Medians and ranges will be presented for T_{max}. Means and standard deviations will be provided for T_{HALF}. Geometric means and coefficients of variation will be presented for C_{max}, C_{trough}, C_{ss}, avg, AUC(TAU), AUC(0-24), CLT/F, V_{ss}/F and AI.

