Each regimen group will consist of 10 subjects. Subjects in each regimen will be randomized and stratified by prior antiretroviral treatment history (ARV naive versus ARV experienced). ARV naive is defined as no prior ARV therapy of ≥ 1 week. Each regimen group will contain approximately the same distribution of ARV naive and ARV experienced subjects. No more than 70% of the total population will be ARV naive or ARV experienced. All regimen groups may initiate dosing simultaneously.

All regimens will be administered under fed conditions. Subjects in Group 2 (QHS regimen group) will receive study drug every 24 hours in the evening from Day 1 to Day 8. Subjects in Group 4 (RTV QAM regimen group) will receive BMS-663068 every 12 hours and RTV every 24 hours in the morning (with BMS-663068) from Day 1 to Day 8. Subjects in Groups 1, 3 and 5 (Q12H regimen group) will receive study drug every 12 hours from Day 1 to Day 8. Plasma HIV RNA levels will be measured before study drug administration on the mornings of Day 1 to Day 8 in groups 1, 3, 4 and 5 and pre-PM drug administration in group 2.

ECG and vital sign assessments will be done at select times during the study. Blood and urine samples for clinical laboratory evaluations will be collected at specified time points throughout the study. Serial blood samples for pharmacokinetic determinations will be obtained on Days 1 and 8 to 11. Blood samples for trough concentrations will be obtained on Days 5 through 7 prior to morning study drug administrations (prior to evening administration for QHS regimen group) for C_{trough} and steady-state assessment. In addition, blood samples for protein binding assay will be collected at specified timepoints throughout the study and selected regimen groups will be analyzed.

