Plasma HIV RNA levels will be measured pre-AM drug administration on the mornings of Day 1 to Day 8 in groups 1, 3, 4 and 5 and Pre-PM drug administration in group 2. On days when dose is not administered, sample collection time should be maintained. Serial blood samples for pharmacokinetic determinations will be obtained on Days 1 and 8-11. Blood samples for trough concentrations will be obtained on Days 5 through 7 prior to morning study drug administrations (prior to evening administration for Group 2, QHS regimen group) for C_{trough} and steady-state assessment. In addition, blood samples for protein binding assay will be collected at specified timepoints throughout the study and selected regimen groups will be analyzed.

Blood for CD4⁺ and CD8⁺ lymphocyte counts and percents and activated (DR⁺) CD4⁺ and CD8⁺ subsets, genotyping, phenotyping, HIV co-receptor usage (CCR5 versus CXCR4), exploratory resistance analysis, measurement of neutralizing antibody activity will be collected at specified timepoints throughout the study. These samples may be analyzed if deemed relevant. Screening samples for population RT/Pol genotyping to confirm that all subjects are infected with clade B HIV will be analyzed in all enrolled subjects. Day 1 predose samples for envelope phenotyping will be collected and analyzed for all randomized subjects.

Approximately 800 mL of blood will be drawn from each subject during the study.

The approximate duration of the study is 88 days. Study participation includes a 35-day screening period, 8-day treatment and 2 follow-up visits.

End of the study will be the date of the last visit of the last subject undergoing the study. Last visit will be the last follow-up visit of a subject.

At the end of the study, the sponsor will not continue to supply study drug to subjects/investigators unless the sponsor chooses to extend the study. The investigator should ensure that the subject receives appropriate standard of care to treat the condition under study.

Table 4.1 summarizes the study design and study parameters.

Table 4.1: AI438006 Study Design

	Regimen Group 1 (N=10)	Regimen Group 2 (N=10)	Regimen Group 3 (N=10)	Regimen Group 4 (N=10)	Regimen Group 5 (N=10)
Dose and Regimen	600 mg BMS- 663068 Q12H + 100 mg RTV Q12H	1200 mg BMS- 663068 QHS + 100 mg RTV QHS	1200 mg BMS- 663068 Q12H + 100 mg RTV Q12H	1200 mg BMS- 663068 Q12H + 100 mg RTV QAM	1200 mg BMS- 663068 Q12H
Days subjects receive BMS-663068	Day 1-8				

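### Section 8.4.4 bases the BMS-626529 steady-state summary in Groups 1, 3, 4 and 5 on troughs after AM doses, but the Day 5 to 7 troughs drawn for it follow PM doses

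*Protocol*

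**What the plan says.** The steady-state analysis of BMS-626529 is set out in one sentence of section 8.4.4. It begins "Time to steady-state will be evaluated by summary statistics of Ctrough (following AM doses except Group 2) by study day" and continues "and by plot of geometric mean Ctrough versus study day". The AM restriction is attached to the summary statistics; the plot clause has none. The synopsis describes the same analysis with no AM or PM restriction at all.

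The sampling is fixed in section 4.1: "Blood samples for trough concentrations will be obtained on Days 5 through 7 prior to morning study drug administrations". The synopsis gives the same morning timing, with the exception and purpose stated as "prior to evening administration for QHS regimen group) for C_{trough} and steady-state assessment". Table 6.5.1A agrees: on Days 5, 6 and 7 it lists a single pre-AM draw for Groups 1, 3, 4 and 5 and no draw before the evening dose.

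Section 8.3.2 defines Ctrough only as "Trough observed plasma concentration", without a dose time.

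**The concern.** In the groups dosed every 12 hours, a sample drawn just before the morning dose is the end of the previous evening's dosing interval. The Day 5 to 7 draws are therefore post-PM troughs, while 8.4.4 asks for post-AM troughs. As written, the analysis leaves out the samples collected for it.

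What remains is Day 1 and Day 8, the same pair that the accumulation index already compares. Two values seven days apart can show a ratio but not a plateau.

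An informal repair carries its own risk. If an analyst simply adds the Day 5 to 7 values to the Day 1 and Day 8 post-AM values, the series mixes dose times. Section 1.3.4 reports a marked diurnal effect on BMS-626529, so a change of dose time along the series could be mistaken for accumulation or decline. The unrestricted plot clause leaves that route open.

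**Working it through.** **Inputs.** Dosing of BMS-663068 every 12 hours on Days 1 to 8 in Groups 1, 3, 4 and 5 (section 4.1), so 8 × 2 = 16 doses. The AM dose of Day d is dose 2d − 1 and the PM dose is dose 2d. Draw times are from Tables 6.5.1A and 6.5.1B. Planned size is 10 per group, so 4 × 10 = 40 subjects.

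**Step 1: assign each end-of-interval sample to the dose before it (Groups 1, 3, 4 and 5).**

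| Sample | Preceding dose | Type |
|---|---|---|
| Day 1, hour 12 | 1 (Day 1 AM) | post-AM |
| Day 5, pre-AM | 8 (Day 4 PM) | post-PM |
| Day 6, pre-AM | 10 (Day 5 PM) | post-PM |
| Day 7, pre-AM | 12 (Day 6 PM) | post-PM |
| Day 8, pre-AM | 14 (Day 7 PM) | post-PM |
| Day 8, hour 12 | 15 (Day 8 AM) | post-AM |
| Day 9, hour 0 | 16 (Day 8 PM) | post-PM |

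That is 2 post-AM and 5 post-PM troughs, 7 in all.

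**Step 2: apply the rule in 8.4.4.** Per subject, 2 of 7 troughs qualify, and 0 of the 3 from Days 5 to 7. Over 40 subjects:

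- inside the summary: 40 × 2 = 80
- outside it: 40 × 5 = 200, of which 40 × 3 = 120 are from Days 5 to 7
- total: 80 + 200 = 280

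**Step 3: Group 2.** There are eight evening doses. Troughs are Day 2 at 24 h (dose 1), pre-PM on Days 5, 6, 7 and 8 (doses 4, 5, 6 and 7) and Day 9 at 24 h (dose 8). All 6 follow a PM dose, and the group is exempt from the AM restriction, so it keeps 6 of 6.

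**Step 4: could the phrase mean sampled in the morning?** Elsewhere in 8.4.4, AM and PM denote the dose:

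- the general summaries run "by regimen group, study day, dose time (AM or PM, Groups 1, 3, 4 and 5 only"
- the inhibitory quotients use Cmax and Ctrough "both on Day 8 following AM regimens except Group 2"; Cmax there can only arise after the AM dose
- the accumulation index is the "ratio of Day 8 [AM doses except Group 2] vs. Day 1 for AUC(TAU), Cmax and Ctrough"

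Consistent use within the section therefore supports the literal reading.

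**Step 5: why the two trough types should not share a series.** Section 1.3.4 reports Cmin about 99% higher after evening than after morning dosing of the 1200 mg extended-release tablet, a ratio of about 1.99. Average AUC-based accumulation in the same section is about 1.3 to 1.5. The measures differ (Cmin against AUC), so the comparison is only indicative. If that ratio held here and the Day 8 post-AM trough were set to 1, a true plateau would appear as about 1.99 on Days 5 to 7 and then 1 on Day 8: a fall produced by dose time alone. Day 8 also has both a pre-AM and a post-AM trough, so study day by itself does not identify one value.

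**The case against.** The strongest reply is that the intent can be recovered. Section 4.1 says which samples serve steady state, and the parenthesis in 8.4.4 has the same shape (morning, except Group 2), so it may be a slip for pre-AM. Table 6.5.1A supports this by marking the Day 5 to 7 draw as 00:00 relative to the last dose, which ties it to the coming AM dose although it falls about 12 hours after the evening one. This is plausible but not decisive, given how 8.4.4 uses AM and PM elsewhere; a slip would still need correcting.

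Second, little is lost. The plot and the synopsis carry no restriction, and the general summary by study day and dose time would still tabulate the Day 5 to 7 troughs. This stands. It means that the counts above describe one table under the literal reading; they do not measure bias or lost precision.

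Third, correcting the phrase to pre-AM would be enough, and a second series is a preference. The diurnal figures in section 1.3.4 answer this: without separation, the Day 1 and Day 8 post-AM values can be mixed with the rest.

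Fourth, the point is specific to BMS-626529. Ritonavir in Group 4 is given only in the morning, so its pre-AM samples do follow an AM dose. That is correct, but the steady-state sentence concerns BMS-626529, and the ritonavir paragraph of 8.4.4 plans no steady-state analysis.

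**Conclusion.** The concern holds, as a minor one. Section 8.4.4 contradicts the sampling schedule for BMS-626529 in Groups 1, 3, 4 and 5: followed literally, the summary statistics for time to steady state rest on 2 of 7 troughs per subject and on none of those from Days 5 to 7. Group 2 is unaffected.

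The counts assume the planned 10 subjects per group, complete sampling and the literal reading of the AM restriction. The mismatch in wording is certain; whether analysts would actually drop the samples is less so, because a drafting slip is possible. No data are lost, the analysis is descriptive and secondary, and the primary endpoint does not depend on it.

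**What to change.** In section 8.4.4, for BMS-626529 in Groups 1, 3, 4 and 5:

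- base the steady-state summary and the plot on the pre-AM troughs (following PM doses) of Days 5, 6, 7 and 8 plus the Day 9 sample 12 hours after the last dose, giving 5 values per subject after doses 8, 10, 12, 14 and 16
- show the 12-hour post-AM troughs of Days 1 and 8 (doses 1 and 15) as a separate, labelled series
- leave Group 2 unchanged, and bring the synopsis sentence into line so that both places name the same series

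The cost is a small text change in two places, a second labelled series in the output, and no new samples. The limit should be stated with it: the main series starts after 8 doses, so it can confirm that a plateau holds from Day 5 but cannot time its onset. Nor can it confirm the impression in section 1.3.4, from earlier data, that steady state is reached within a day of starting. Before Day 5, onset stays unobserved on a like-for-like basis in these four groups.
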